## 5.3 Evaluation Participants

### 5.3.1 Inclusion Criteria

The evaluation will include participants who meet the following criteria:

- Pregnant women aged 16 or over, who reside in the evaluation intervention and comparison area wards (identifiable by postcode).

### 5.3.2 Exclusion Criteria

The following individuals will be excluded from the study:

- Women who are not pregnant
- Pregnant females who reside within the evaluation intervention or comparison wards, but are aged less than 16 years
- Pregnant women who have been involved in the pilot study or in the cohort study, with a previous child
- Pregnant women who do not reside in the evaluation intervention or comparison area wards
- Pregnant women who reside in one of the evaluation area wards, but are suffering from severe mental illness (e.g. psychosis)
- Women who know they are moving away from an evaluation area within the first 6 months of the beginning of the study

## 5.4 Recruitment and Informed Consent

### 5.4.1 Baseline Recruitment

In addition to the main longitudinal cohort study the evaluation will collect baseline data from each of the participating sites prior to the introduction of ABS. This will involve administering the 1; 2 and 3-year face-to-face survey with a sample of parents of 1; 2 and 3 year old children at one time-point only. These families will not be involved in the main cohort study, and their data will be used to provide an indication of the level of parent and child wellbeing in the sites prior to implementation of A Better Start. This will provide the evaluation with a set of baseline measures for children aged 1, 2 and 3 years.

A short piloting of baseline questionnaires will take place prior to the main baseline survey. Parents will be identified using a commercial sampling frame called Emma's Diary and, based on results, this sampling frame will most likely be used to identify parents eligible to take part in the main baseline survey.

Emma's Diary is the largest pre-natal database in the UK and collects c. 650,000 records each year. It has been used as a sampling frame for other studies, including research into pregnancy discrimination at work for the Equal Opportunities Commission and in an evaluation conducted by evaluation partners Bryson Purdon Social Research for the NSPCC. However, in order to ascertain whether this sampling frame will provide appropriate coverage and response rates for this evaluation, a review of the viability of using Emma's Diary for the main baseline survey will be undertaken following the pilot, and recommendations made for further discussion by the Consortium.

Emma's Diary is a communication platform for mothers-to-be, new parents and healthcare professionals. In association with the Royal College of General Practitioners, Emma's Diary offers a programme of targeted communications, providing advice and health information. It produces a pregnancy guide, which is distributed to women through GP surgeries, generally on their first visit to the doctor/midwife regarding their pregnancy. This guide also contains information on how women can register with Emma's Diary in order to receive gift packs of free baby products. Parents who

---

 <http://www.maternityaction.org.uk/wp/wp-content/uploads/2013/09/eocpregnancydiscrimwomensurvey.pdf>

 <http://www.nspcc.org.uk/globalassets/documents/evaluation-of-services/evaluation-preventing-non-accidental-head-injuries-nahi-programme-impact.pdf>

sign up to Emma's Diary give their consent for other organisations to contact them by post, telephone, SMS or email about selected products, services and research.

The process for sample selection and recruitment will be as follows:

1. Ipsos MORI field team will send an advance mailing to selected mothers registered with Emma's Diary for the purpose of piloting of the baseline questionnaires. The standard invitation letter will explain the nature and aims of the study and why mothers are being invited to take part. The letter will also explain that a study researcher will contact them shortly in person to discuss the study further, and to ask if they wish to take part.
2. Along with the advance mailing, the potential respondents will also be provided with:
  - A full information sheet about the study. This information sheet will state clearly to potential respondents that they have been contacted due to giving permission when registering with Emma's Diary.
  - An opt-out form and return pre-paid envelope so the potential respondent can tick a box to indicate they wish to opt-out, rather than having to call or email and/or feeling that they have to provide any explanation.
3. In order to provide reasonable time to opt-out, Ipsos MORI will give potential respondents a minimum of 2 weeks before making contact to invite them to take part in the baseline pilot survey (which involves a face-to-face interview);
4. The subsequent contact from Ipsos MORI to the potential respondent to discuss the study will be made face-to-face, rather than by telephone. Interviewers will gently check that the child is living at home and well, and will be better placed by being there in person to deal with any sensitive situations in an appropriate way.
5. If at that time the respondent agrees, the researcher will make a time to visit, obtain written informed consent and conduct the interview.

The same procedures will be followed for the main baseline survey.

Ipsos MORI has a strong track record in surveys with families, which means that its interviewers are very experienced in engaging and working considerately with this type of audience. All interviewers working on this study will attend a briefing day specifically about this survey before they start work, and this will include a section about how to handle a situation where they are communicating with a family who have lost their baby or have major problems.

It should be noted that the sample provider, Emma's Diary, run their data through the Baby Mailing Preference Service (MPS) on a weekly basis. The Baby MPS is a free service that can be signed up to in order to reduce number of baby-related mailings received. This service is particularly aimed at families who have experienced the sad circumstances of the death of a baby.

Interviewers are accompanied by an experienced supervisor when starting work on a new project, and received on-going telephone support throughout the study duration

Before starting work in an area, interviewers are advised to check-in at the local police station to show their ID cards and advise local police they will be working in the area for a specified period of time.

#### 5.4.2 Main Cohort Study Recruitment

##### *Participant Identification and Providing Permission to be Contacted*

Participants eligible to take part in the evaluation will be identifiable by their postcode by a member of their relevant local NHS Trust maternity team at the time of booking (at approximately 9-12 weeks' gestation). A Participant Information Sheet (PIS), containing all information about the evaluation (in a potential respondent's native language where possible), will be given to her in person or posted out to her at this time, along with standard antenatal information.

Working within the existing systems and processes of individual participating Trust maternity (or Health Visiting) teams and the available resources within each, eligible pregnant women will subsequently be asked by a member of their maternity and/or research team (for instance, this may be a midwife, research midwife, researcher, Clinical Trials Assistant (CTA) or Healthcare Assistant (HCA) or any other trained team member) if they have received and read the evaluation

---

 Additional permission will be sought to **retain** participants' contact details should the research team wish to re-contact them regarding any future follow-up research (refer to Section **5.1.1 Potential Additional Data Collection**).

information. The team member will provide the information again if it has been misplaced or has not been received, and will take a few minutes to run through the PIS and answer any questions the potential respondent may have. Subsequently, if the potential respondent is happy to provide signed permission for her contact details (preferably name, address, telephone number and/or email) to be passed on to the Ipsos MORI research team, she and the team member will complete the form together and sign it. This is then either uploaded and transferred securely electronically (encrypted) to Ipsos MORI, or by using the pre-paid addressed envelopes provided. A copy of the signed permission to be contacted form is maintained within the potential respondent's notes.

Once received, Ipsos MORI will cross-check that the postcode matches to one of the intervention wards or matched comparison wards of interest and that the woman is therefore eligible for inclusion. Ipsos will email the evaluation Project Manager at the University of Warwick and Oxford a password protected file of any ineligible participants in order that she can send them a letter acknowledging their commitment to take part and thanking them for their time. Thus, the evaluation Project Manager will also have access to some Personal Data (see Section 9 for details of data management and security).

Ipsos MORI will check with the designated named individual at each Trust (see Section 5.4.5) that the woman is still pregnant prior to contacting her. This process will be repeated during the main longitudinal evaluation starting January 2019 prior to contacting any woman at or around the time of birth who has been randomly selected to provide a biological sample.

Only if permission is granted, an Ipsos MORI researcher will contact the woman - by writing or telephone and/or in person – to discuss the evaluation and answer questions, and ask if she is still happy to take part in the study; if so, a first face-to-face appointment will be scheduled to take place when the woman is approximately 26 - 36 weeks pregnant. This interview may occur at a time and place convenient to her. If she does not feel comfortable about the meeting taking place in her home, she may request to meet at a friend or family member's, or in a local Children's Centre etc. Informed consent is taken by the Ipsos MORI researcher prior to conducting the interview and a copy of the consent form is retained by Ipsos MORI, a copy retained by the respondent. A third copy is sent securely (encrypted) by Ipsos MORI to the respondent's maternity contact.

The relevant NHS Trust will receive one accrual for each pregnant women who provides informed consent and takes part in the antenatal interview. The Trust will also receive an additional accrual for each neonate (but not the mother) who provides a buccal (cheek) swab (see section 5.4.6.1)

Please note that completing a *Permission to be Contacted* Form to be passed on to Ipsos MORI is *not* informed consent, and is therefore *not* a commitment to take part in the study. When she is later contacted by Ipsos MORI, the potential respondent is completely at liberty to refuse to take part in the study and, even if she agrees, provides her consent and takes part in the antenatal survey, she can withdraw at any time over the life of the study.

### 5.4.3 Post-Recruitment Participant Exclusions and Withdrawals

#### *Post-Recruitment Exclusions*

As a result of the fact that the evaluation is focusing on specific intervention areas and comparing these with the outcomes of families receiving standard services in comparison areas, families will be excluded from the evaluation post-recruitment if:

- They do not go on to have a live birth
- They move away from the evaluation intervention or comparison areas after the evaluation has begun
- They move into the evaluation intervention and comparison areas after the evaluation has begun
- Their participating child is taken into care, but only where informed consent from the appropriate authority for the child to continue in the evaluation cannot be obtained

#### *Post-Recruitment Withdrawals*

Families may withdraw from the evaluation as they wish, at any time. Sample sizes have been designed to take into account attrition rates over the evaluation period. Withdrawal from the study will not affect the participant's entitlement to intervention services in any way.

#### 5.4.4 Recruitment for the School-based Data Collection

Schools will be recruited via Head Teachers within both the intervention and comparison areas (and will also be sent a letter by their local authority requesting support for the research). For the age 5 data collection points, they will be sent a pack of standardised survey materials, including the teacher questionnaires, and parental consent forms. Guidance on completion will be provided at each time-point by a University of Oxford researcher by telephone.

#### 5.4.5 Piloting of the Recruitment Process

Beginning in early 2016, a small pilot study will be undertaken across each of the five ABS programme areas, and one comparison area for each of these areas – 10 areas in total - to test the methodology for recruitment and optimal response rates for the first two postnatal survey completion options. Families will be followed up until the 4-month postnatal time-point only, schedule permitting.

All of the procedures being used in the main cohort study will apply, but parents will be informed that they are taking part in a pilot study, prior to the commencement of the main study. This will also provide the research team with the opportunity to pilot the data collection procedures.

The team has discussed concerns regarding potential late foetal loss when consent for contact details may be taken and passed on to Ipsos MORI, and; the 26-36 weeks antenatal Participant Informed Consent being taken and first interview conducted by Ipsos MORI. In order to avoid causing further undue distress by unknowingly contacting a woman who may have suffered a late foetal loss, the evaluation team has discussed with NHS Trust midwifery teams, implementing the following process:

- Approximately 1 week prior to the 26-36 weeks antenatal fieldwork starting, using a previously arranged named single contact, Ipsos MORI will email each NHS Trust maternity unit a password-protected sample file of the names and addresses of potential participants identified by the midwives at that Trust, and who agreed to pass on their contact details. Each individual within this sample will be allocated a unique reference number;
- The key maternity contact at each unit will be asked cross-check these details against his or her '*no-longer pregnant database*' (administered by all maternity units), and to respond to Ipsos MORI by email within c. 5-7 working days, sending the *reference numbers only* of women they *do not* wish Ipsos MORI to contact. The maternity unit key contact *does not* have to divulge any personal or confidential information; however, the Consent for Contact Details and Study Consent Forms relating to both pilot study and main evaluation, have now been amended to include an additional clause giving the potential respondent a choice about whether she may permit her midwife or other healthcare professional known to her contact the study team should she no longer wish/be unable to be involved due to '*medical reasons*'.
- If Ipsos MORI *does not* receive any response, *all* women within that sample will be contacted;
- If Ipsos MORI *is* notified of any women who should not be contacted, the field team will be informed immediately and these individuals *will not* be sent an advance mailing.

Trusts will also undertake their own screening on a routine basis as per their own standard protocols, and will inform Ipsos MORI in between times should they become aware of a woman who should no longer be contacted. Unfortunately, after a mother and baby are discharged from the Trust alive and well, there is no further screening mechanism that can be implemented after this time.

#### 5.4.6 Informed Consent

Written and confirmed consent to take part in the evaluation will be sought at the time of, but prior to, conducting the first 26-36 weeks' antenatal face-to-face interview.

- Informed Consent will be sought as follows:
- From the **mother only** to take part in either the pilot of recruitment methodology or the main evaluation;
- Additionally, from the **resident** partner/father, should he wish to complete the existing short partner questionnaires scheduled to be completed at 26-36 weeks' pregnancy and again when the child reaches ages 1, 2 and 3 years.

---

 Where local R&D approval has not been issued as quickly as expected, it may only be possible to follow-up participants in these areas to the 26-36 week gestation or 2-month postnatal time-point, rather than to 4-months postnatal as originally intended.

 If a mother (assuming the role of primary carer) and the partner disagree about taking part in the study or this causes any conflict, the mother will in no way be persuaded to participate.

- Additionally, for permission to retain the details of **the mother to re-contact** her about any future follow-up research (refer to Section **5.1.1 Potential Additional Data Collection**);
- **Verbally** for continued participation in the evaluation at each face-face interview (when child is aged 1, 2 and 3 years).

**Consent can be withdrawn at any time.**

#### *Informed Consent for Sub-Samples*

Additional written informed consent will be sought for the randomly selected biometric sub-sampling procedures at birth (i.e. consent will be taken by a GCP-trained member of the NHS maternity/health visiting unit at or around the time of birth (up to 4 weeks after the birth), to take a hair sample from the mother and a buccal (cheek) swab from the baby).

Accruals will be provided to the Trust for both the mother providing informed consent and taking part in the antenatal survey (but not again by agreeing to provide a hair sample at birth - see section 5.4.2). However, her baby can be counted as one additional accrual by the Trust by providing a cheek swab at birth.

Separate verbal consent will be sought for the Ipsos MORI researcher to take a sub-sample from these same families when the child is aged 2 years (hair sample and a cheek swab from the child), and from the same or other randomly selected families at age 1 (CARE index) and by the University of Oxford researcher, who will take a sub-sample of the Manchester Child Attachment Story Task (MCAST) in school when the same or other children are aged 5-years. The mother may refuse to give consent for any of the sub-sampling procedures at any time even if she has previously consented, or to complete all of the questionnaires; this does not affect the right of she and her child to remain in the study.

#### *Informed Consent for the School-based Data Collection*

Parents will be asked at the age 3 interviews for details of the school likely to be attended by their child, and for consent for the research team to contact the school. Parents who do not know the child's intended school at age 3 will be asked for consent to be re-contacted at age 4 in order to obtain this information. Consent for data collection at age 5 will also be obtained at this time (i.e. at age 3 where parents know the school, at age 4 when they do not). However, since this will represent the last point of direct contact with parents, parental consent for data collection at age 6 will be obtained via teachers in the schools at the time of the age 5 teacher survey.

The evaluation has been designed to predominately follow the progress and outcomes of the child. If a child taking part in the evaluation were subsequently removed from the care of the mother, or the mother dies etc., then informed consent would be sought from the child's primary carer or guardian to continue in the evaluation.

## 5.5 Sample Size

### 5.5.1 Baseline Surveys

A total of 899 interviews will take place across all ABS programme areas and 802 across all fifteen comparison areas, with a breakdown as follows (c.1701 in total):

Parents of children aged 1, 2 and 3 years:

- Programme areas: 378 children aged 1; 313 children aged 2; 208 children aged 3
- Comparison areas: 225 children aged 1; 361 children aged 2; 216 children aged 3

### 5.5.2 Main Cohort Evaluation Surveys

The primary research question will be addressed using a longitudinal cohort study in which a target of 2,885 pregnant women across the five intervention and fifteen matched comparison areas will be recruited to the study. Further detail is provided in Table 2.

**Table 2. Cohort Survey Sample Sizes**

Survey Time Point	ABS (Programme) Area	Comparison (Matched Control) Areas
26-36 weeks' antenatal	1715	1170
Child Aged 1 Year	1200	825
Child Aged 2 Years	1060	720
Child Aged 3 Years	815	555

### 5.5.3 Sample Size Justification

The sample size for the cohort study has been set with the primary aim, after attrition, of generating 815 interviews with parents of three year olds in programme areas and 555 in comparison areas. The 'headline' estimates of impact will be based on difference-in-differences estimates. That is, change since baseline for children of the same age group in ABS areas, minus change since baseline in comparison areas. For outcomes at age 1, for instance, this will be based on the four sets of data within the second row of the table (i.e. 500; 270; 1200; 825). Samples of this size will enable detection of effect sizes of 0.25 standard deviations (with 80% power). For binary outcomes, this equates to being able to detect an impact of around 12 percentage points (i.e. if 12% of children in ABS areas have a better outcome at age 1 as a direct result of the programme, a difference-in-difference estimate should be observed that is significantly different to zero). At Age 2 the cohort sample sizes will have been subject to attrition, and the detectable effect size at age 2 will be just over 0.25; and with further attrition at Age 3, the detectable effect size will be 0.26.

In practice, it is hoped that no real differences in the baseline outcomes for ABS and comparison areas will be observed. If baseline differences can be ruled out, then the evaluation can focus on comparing the ABS and comparison cohort samples. This will greatly improve the statistical power. For example, at age 1, if only the two cohort samples of 1200 and 825 were compared, effect sizes of 0.13 standard deviations could be detected.

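### The detectable effects for the headline difference-in-differences estimate rest on baseline samples of 500 and 270 that the protocol does not have; with its own baseline numbers the age-3 figure is 0.31 SD, not 0.26

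*Protocol*

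**What the plan says.** Protocol section 5.5.3 defines the headline estimate of impact as "change since baseline for children of the same age group in ABS areas, minus change since baseline in comparison areas". It therefore uses four independent samples: baseline and cohort, in programme and comparison areas. For age 1 the section says "this will be based on the four sets of data within the second row of the table (i.e. 500; 270; 1200; 825", and then "Samples of this size will enable detection of effect sizes of 0.25 standard deviations (with 80% power". It equates this to roughly 12 percentage points for a binary outcome. For age 2 it puts the detectable effect slightly above 0.25, and for age 3 it says that "with further attrition at Age 3, the detectable effect size will be 0.26"; cohort attrition is the only reason it gives for the increase. The same section states that the cohort was sized primarily to yield 815 and 555 interviews at age 3.

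Section 5.5.1 gives the baseline samples by age: "Programme areas: 378 children aged 1; 313 children aged 2; 208 children aged 3" and "Comparison areas: 225 children aged 1; 361 children aged 2; 216 children aged 3". These add up to the totals stated there (378 + 313 + 208 = 899; 225 + 361 + 216 = 802). Table 2 lists cohort sizes only: 1200 and 825 at age 1, 1060 and 720 at age 2, 815 and 555 at age 3.

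**The concern.** The table cited in section 5.5.3 does not contain 500 or 270, and no age group in section 5.5.1 has a baseline of that size. In a difference-in-differences the variance is the sum of four terms, and the smallest samples dominate it. Here those are the baseline samples, so overstating them directly understates the detectable effect. The programme baseline falls from 378 at age 1 to 208 at age 3, so the error is likely to be largest at age 3. That is the age used for sizing and one of the two ages named in the first hypothesis (section 4.2). At stake is whether the headline estimate has the 80% power claimed for it. A reader who takes 0.26 SD as the effect the study can detect at age 3 would also misjudge what a non-significant result means.

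**Working it through.** **Inputs.** Power of 80% is stated in section 5.5.3. The significance level is not. The text refers to an estimate "a difference-in-difference estimate should be observed that is significantly different to zero", and I assume two-sided 5%. Outcome SD is 1, the four samples are independent, and no design effect is applied.

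**Formula.** Detectable effect = (1.960 + 0.842) × √(1/n₁ + 1/n₂ + 1/n₃ + 1/n₄) = 2.8016 × √(sum of reciprocals).

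**Reproducing the protocol's figures**, with baselines of 500 and 270 at every age and the Table 2 cohort sizes:

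- Age 1: 1/500 + 1/270 + 1/1200 + 1/825 = 0.007749; 2.8016 × 0.08803 = 0.247 (stated 0.25).
- Age 2: 1/500 + 1/270 + 1/1060 + 1/720 = 0.008036; 2.8016 × 0.08964 = 0.251 (stated just over 0.25).
- Age 3: 1/500 + 1/270 + 1/815 + 1/555 = 0.008732; 2.8016 × 0.09345 = 0.262 (stated 0.26).

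The cohort-only figure at age 1 also reproduces: 2.8016 × √(1/1200 + 1/825) = 0.127 (stated 0.13). A one-sided 5% test would give 0.219, 0.223 and 0.232, and 90% power would give 0.285, 0.291 and 0.303; neither fits. The method and significance level are therefore identified. The protocol names 500 and 270 for age 1 only. That they were carried over to ages 2 and 3 is an inference, supported by the match at age 3.

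**With the section 5.5.1 baselines:**

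| Age | Baseline (programme, comparison) | Cohort (programme, comparison) | Sum of 1/n | SE | Detectable effect | Stated |
|---|---|---|---|---|---|---|
| 1 | 378, 225 | 1200, 825 | 0.009135 | 0.0956 | 0.268 | 0.25 |
| 2 | 313, 361 | 1060, 720 | 0.008297 | 0.0911 | 0.255 | just over 0.25 |
| 3 | 208, 216 | 815, 555 | 0.012466 | 0.1117 | 0.313 | 0.26 |

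**Power at the stated effects**, Φ(d/SE − 1.960):

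- Age 1, d = 0.25: Φ(2.616 − 1.960) = 74%.
- Age 2, d = 0.25: Φ(2.745 − 1.960) = 78%.
- Age 3, d = 0.26: Φ(2.329 − 1.960) = 64%.

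**Binary outcomes.** Near 50% prevalence (assumed) the SD is 0.5, so the detectable difference is half the effect size. With 500 and 270 at age 1 this is 12.3 points, in line with the protocol's figure of about 12. With the section 5.5.1 baselines it is 13.4, 12.8 and 15.6 points at ages 1, 2 and 3.

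**Where the loss at age 3 comes from.** The two baseline terms are 1/208 + 1/216 = 0.009437, which is 76% of 0.012466. Alone they give 2.8016 × √0.009437 = 0.272. Even an unlimited cohort could not reach 0.26 SD with 80% power. The constraint is the baseline, not the attrition to which the text attributes it.

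**The case against.** Four points can be made for the protocol.

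First, the age-2 statement survives: 0.255 is still just over 0.25, and age 1 is only modestly out. That is right. The material error is the age-3 figure.

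Second, section 5.5.3 says that if baseline differences can be ruled out, the evaluation can compare the cohort samples alone. At age 3 that comparison detects 2.8016 × √(1/815 + 1/555) = 0.154 SD, whatever the baseline size. Section 6.2 also leaves the choice of datasets to a plan written before each analysis phase. This softens the consequence but does not correct the figure. Difference-in-differences remains the headline, and the alternative depends on ruling out baseline differences. At age 3, 208 against 216 families has 80% power only for a baseline difference of about 0.27 SD, which is weak ground for ruling out smaller ones.

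Third, nothing in the protocol says that a null result would be judged against the planning figure; the confidence interval would govern. That is fair. The case here rests on the misstated power, not on a predicted misreading.

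Fourth, the recomputed values are simple-random-sampling figures and not the final precision. That is true, but the protocol's own figures are on the same basis. Section 6.2 says standard errors will reflect matching, non-response weights and between-area effects. If these raise the variance, 0.313 is a best case.

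**Conclusion.** The point holds. Section 5.5.3 is inconsistent with section 5.5.1 and with Table 2, and the stated power for the headline estimate is not delivered at two of the three ages. The detectable effect at age 3 is about 0.31 SD where the text says "with further attrition at Age 3, the detectable effect size will be 0.26", an understatement of roughly 0.05 SD, with 64% power at the stated effect. At age 1 it is about 0.27 instead of 0.25, with 74% power. At age 2 the stated figure is acceptable. These results assume a two-sided 5% test, which the protocol does not state but which reproduces its figures, and no design effect. Because the largest error is at the age for which the cohort was sized, the section should be corrected before its power statement is relied on.

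**What to change.** In section 5.5.3, replace the 500 and 270 with the section 5.5.1 baseline numbers and set out the four sample sizes for each age. Restate the difference-in-differences detectable effects as about 0.27 (age 1), 0.26 (age 2) and 0.31 SD (age 3), with binary equivalents of about 13.4, 12.8 and 15.6 percentage points near 50% prevalence. State the two-sided 5% level and that the figures are before any design effect. Say that the age-3 figure is driven mainly by the baseline sample size, not only by cohort attrition. Add baseline columns to Table 2, so that the reference to its second row points to numbers that are there; a cross-reference to section 5.5.1 would also serve. If 500 and 270 are the intended baseline sizes, section 5.5.1 is what needs correcting; either way the two sections must agree.

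Adopting the section 5.5.1 numbers costs protocol wording only. No cohort target, estimator or procedure changes, but the stated figures become less favourable.
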